Title: POM-HR (Post Operative Morbidity- heart rate): Observational study of exercise-induced heart rate dynamics and their relationship to postoperative morbidity.

Short title: POM-HR

Objectives: Primary objective: To assess whether abnormal heart rate dynamics following cardiopulmonary exercise testing is related to postoperative complications and length of hospital stay.

Secondary objective: To assess whether abnormal heart rate dynamics following cardiopulmonary exercise testing is related to immune-inflammatory phenotypes and structural heart differences.

Type of trial: Unblinded, two-site, observational retrospective and prospective studies in elective surgical patients undergoing cardiopulmonary exercise testing (CPET) as part of their routine preoperative workup.

Trial design and methods: Retrospective study: Anonymized data detailing cardiopulmonary exercise tests and postoperative morbidity/ length of stay that are collected and assessed routinely as part of clinical care will be provided by both centres.

Prospective study: Preoperative patients undergoing major surgery are referred routinely for

cardiopulmonary. All heart rate data is derived from cardiopulmonary exercise testing acquired data, performed as part of their routine preoperative workup.

Blood derived immune cells will be acquired at UCLH site only pre and post exercise from from indwelling catheters routinely placed for the CPET itself.

Transthoracic (non-invasive) echocardiography will be performed pre and post CPET at the UCLH site only.

Postoperative morbidity and complications will be recorded on days 3, 5, 7, 10 and 14 if the patient remains in hospital for that length of time. This is routinely collected in both hospitals.

Trial duration per participant: 6 weeks, including duration between consent CPET and end of surgical hospital stay.

[figure not shown]
Estimated total trial duration: 4 years

Planned trial sites: University College London Hospital;
Derriford Hospital, Plymouth

Total number of participants planned: 1356

Main inclusion criteria: All surgical patients referred for cardiopulmonary exercise testing preoperatively by their surgical or anaesthetic consultant undergoing major noncardiac surgery.

5. Flowchart of events:

6. Background

Hypothesis

To demonstrate that autonomic dysfunction (as reflected by heart rate response to exercise) is predictive of short-term postoperative morbidity and length of stay.

Background

Complications following surgery are an important cause of morbidity and mortality. When these complications occur within 30 days of major surgery a patients' long term survival may be compromised [1]

Heart rate recovery is an independent predictor of longer term cardiovascular disease outcomes. Beyond the heart, the vagus nerve plays important roles in reducing inflammation and protecting cells from various stresses. The rate of heart rate recovery following exercise reflects how well the vagus nerve works. Standardized exercise tests allow us to measure how well the vagus nerve is working, and therefore provide important insights into whether the vagus nerve helps protect cardiac function and noncardiac effects in different patients undergoing major surgery. POM-HR is a mechanistic study designed to examine if abnormal heart rate recovery can identify patients who are at greater risk of complications post-operatively through abnormal autonomic activation. Studies have suggested that the central nervous system controls the body's response to inflammation. The vagal nerve is an important nerve in the central nervous system and has an influence on organs such as the spleen and liver which help dampen down inflammation. Experimental model studies have shown that signals via the vagal nerve can inhibit inflammation and improve outcomes in various disease processes including models of sepsis, myocardial ischaemia and ileus.[5-13] Understanding this mechanism in a clinical context may help us to understand why some patients sustain complications after surgery. This will allow future clinical care to be guided by an understanding of why these complications arise and allow early detection, treatment and avoidance of postoperative morbidity.

7. Purpose

There is a need to confirm that a vagal neuro-immune activation is linked to postoperative complications. Demonstrating that a vagally controlled neuro-immune activation is linked to reduced postoperative complications in surgical patients will enhance our understanding of the underlying

mechanisms. This investigation could then encourage a widespread use of simple interventions, such as preoperative exercise regimes, to enhance vagal activation following all types of surgery to reduce morbidity postoperatively.

8. Study design

For the retrospective study, pre-existing nonidentifiable morbidity and preoperative cardiopulmonary exercise test data is acquired as part of the clinical quality monitoring at both hospitals and can be provided by the clinical care teams thus ensuring no breach of confidentiality. These data are fully anonymised and do not include any potential identifiers.

For the prospective study: All heart rate data is derived from cardiopulmonary exercise testing acquired data, performed as part of their routine preoperative workup. Blood derived immune cells will be acquired at UCLH site only pre and post exercise from from indwelling catheters routinely placed for the CPET itself. Ex-vivo laboratory studies will explore bioenergetic (mitochondrial) function in leukocyte subsets and Immune function in leukocyte subsets. Transthoracic (non-invasive) echocardiography will be performed pre and post CPET at the UCLH site only. Postoperative morbidity and complications will be recorded on days 3, 5, 7, and 14 if the patient remains in hospital for that length of time. This is standard practice in both hospitals.

UCLH has a strong record of perioperative research in this area. As such our local patients are fully engaged in the perioperative research process. Our Critical Care patient liaison group is a strong advocate of patient centred outcomes research. We also have patient representatives via the Centre for Anaesthesia Patients Information Group, who participate in our monthly clinical research meetings to present patient views on research, protocols and enrolment issues (<http://www.ucl.ac.uk/anaesthesia/patients>).

9. Selection of subjects and Informed consent procedure

Recruitment

Patient recruitment will only be done when the trial has

1. Documented REC, Regulatory and Local Trust R&D approval
2. A signed site agreement
3. The site has sent back to the TC the PI self-monitoring template.

10. Subject selection

Inclusion criteria

All surgical patients referred for cardiopulmonary exercise testing preoperatively by their primary surgeon or anesthesiologist undergoing major noncardiac surgery.

Exclusion criteria

1. history of exercise induced angioedema,
2. pregnancy,
3. any contraindication to cardiopulmonary exercise testing (as outlined by American Association of Anaesthesia):

Consent procedure

For the retrospective study, we have written confirmation from the NIGB ([name], Ethics and Confidentiality Committee; [contact]) that nonidentifiable morbidity and preoperative cardiopulmonary exercise test data can be provided by the clinical care teams thus ensuring no breach of confidentiality. Pre-existing nonidentifiable morbidity and preoperative cardiopulmonary exercise test data is acquired as part of the clinical quality monitoring at both hospitals and can be provided by the clinical care teams ensuring no breach of confidentiality. These data are fully anonymised and do not include any potential identifiers. It is the responsibility of the principal investigator and co-investigator to ensure written informed consent from each subject prior to participation in this study. Responsibility for conducting the informed consent process may be delegated to appropriately trained members of the research team (see 18. definition of responsibilities). This process will include an explanation of the aims, methods, anticipated benefits and potential hazards of the study. The CPET service will highlight potential patients ahead of their attendance at surgical clinic, several weeks before the initiation of the study. No healthcare professionals involved in the patients perioperative care will be involved in the consent process. The principal investigator and co-investigator will explain to all potential participants that they are free to refuse to enter the study or to withdraw at any time during the study, for any reason. The patients will be approached prior to the CPET, thereby affording suitable time for patients to consider the process of consent. The principal investigator and co-investigator

will be contactable by mobile phone and electronic mail to address further queries. Where a patient wishes to be withdrawn from the study, only the primary outcome data will be collected to enable intention treat analysis. Non-English speakers will be provided with full access to NHS translation services to ensure appropriate understanding of the trial and consent process. We will not recruit patients who lack capacity to give or withhold informed consent. A copy of the signed Informed Consent will be given to the participant. The original signed form will be retained at the study site.

11. Risks, burdens and benefits

Risks and burdens

There are no study specific risks introduced by this study since we are utilizing preoperative data from routine investigations and postoperative outcomes. CPET preoperative investigation represent routine care at UCLH and Derriford hospitals. Post Operative Morbidity Survey data is routinely collected at UCLH and Derriford, so represent standard of care at our institutions.

Benefits

1. The information we get from this study may help us to better treat future patients undergoing surgery and those who are seriously ill in intensive care.

12. Randomisation

Observational study- not applicable.

13. Definition of end of trial

The end of the trial will be the date of the last visit by the last participant.

14. Conflicts of Interest

There are no conflicts of interests for this study. After the study has ended, the results will be fed back to all participants and patient representatives via the Centre for Anaesthesia Patients Information Group, which we invite to participate in our monthly meetings.

Use of tissue samples in future research

Samples will be stored securely within Wolfson Institute for Biomedical Research, UCL. These samples will be used to investigate cellular processes that may be involved in perioperative complications. The CI is the only investigator authorized to use these samples. All subsequent amendments will be notified.

15. Data management and quality assurance

Confidentiality/data handling and analysis

For the retrospective study, we have written confirmation from the NIGB ([name], Ethics and Confidentiality Committee; [contact]) that nonidentifiable morbidity and preoperative cardiopulmonary exercise test data can be provided by the clinical care teams thus ensuring no breach of confidentiality. These data are fully anonymised and do not include any potential identifiers. Submitted data will be coded (pseudoanonymised) and reviewed for completeness and consistency and then entered on a database. To ensure validity and quality, double data entry will be performed.

All data collection will be recorded on case report forms (CRF) embedded in access database, located on secure, password protected and encrypted (NHS mandated "Ironman") USB keys. Data is stored securely against unauthorised manipulation and accidental loss. Desktop security is maintained through user names and frequently updated passwords and back up procedures are in place. All essential documents and trial records will be archived in conformance with the applicable regulatory requirements and access to these archives will be restricted to authorised personnel. Data will be secured in pre-existing, locked and password protected facilities within the Wolfson Institute for Biomedical Research, UCL or the Anaesthetic Research Office, Terence Lewis Building, Derriford Hospital, Plymouth. Records will be retained in this secure location for retention – duration and location. All data collection, storage and access will adhere to the Data Protection Act 1998. Dr

[name] (UCL) & [name] (Plymouth) will be responsible for data collection, recording and quality. In-house audits of data quality will be performed throughout the trial. Site monitoring visits will involve source data verification. The Case Report Forms (CRFs) will not bear the subject's name or other personal identifiable data. The subject's initials, date of birth and trial identification number, will be used for identification.

The code for a particular subject may be broken in a medical emergency if knowing the identity of the treatment allocation would influence the treatment of the subject or if demanded by the subject. Whenever a code is broken, the person placing the call will be requested to sign the fax from UCLH CTU and add the reason for breaking the code. This document is Source Data and should be kept with the CRF. Relevant persons (i.e. the investigator will get access to the UCLH CTU "code breaking call" via an access and pin code supplied by UCLH CTU. If the trial needs to break the code, the Sponsor should, if possible, be contacted prior to breaking the code. In all cases, the Monitor must be notified within 24 hours after the code has been broken. All codes (whether broken or not) must be kept throughout the trial period. Accountability of all codes (hard copy or electronic) will be performed at or after trial closure and will be collected by the Monitor.

Participant safety and wellbeing are protected by implementation of the sponsoring organisation's standard operating procedures (SOPs) as set out in the Research Governance Framework and The Medicines for Human Use (Clinical Trials) Regulations 2004. As sponsor UCLH/UCLH performs regular audits of research and this study may be selected for such an audit. Systems are in place to ensure that all investigators are able to demonstrate that they are qualified by education, training or experience to fulfil their roles, and systems and procedures are in place which can assure the quality of every aspect of the trial. If new safety information becomes available, then study participants will be informed of this and asked if they wish to continue in the study. If the subjects wish to continue in the study they will be formally asked to sign a revised approved participant information sheet and consent form. Day to day management will be undertaken via a trials management group composed of the principal investigator and supporting staff. They will meet on a weekly basis to discuss study issues. Site monitoring will be directed by the sponsor according to the study risk analysis.

Data collection tools and source document identification

Case report forms will be designed and produced by the investigator, according to the sponsor's CRF template. The final version will be approved by the sponsor. All data will be entered legibly in black ink with a ball-point pen. If an error is made, the error will be crossed through with a single line in such a way that the original entry can still be read. The correct entry will then be clearly inserted,

and the alterations will be initialled and dated by the person making the alteration. Overwriting or use of correction fluid will not be permitted.

It will be the responsibility of the investigator to ensure the accuracy of all data entered in the CRFs. The delegation log will identify all those personnel with responsibilities for data collection and handling, including those who have access to the trial database.

Transfer of data from Derriford to UCL

Data will be entered from paper CRFs onto access database by responsible investigator(s) at the Derriford study site. Participants will be identified by study number only so that confidentiality will be maintained. The access database will be sent by secure nhs email from the Principal Investigator at Derriford to the Chief Investigator at UCL. Thus no patient identifiable data will leave the Derriford site.

Record Keeping and archiving

Chief Investigators are responsible for the secure archiving of trial documents and the trial database.

16. Statistical analysis

Statistician involved in powering the study: [name], Department of Health Services Research and Policy, Institution London School of Hygiene + Tropical Medicine
[name]. [contact]

Surgical Patients – Sample size

Primary outcome is incidence of morbidity on postoperative day 5. 40% of patients undergoing major surgical procedures sustain defined morbidity on postoperative day 5. From the cardiovascular literature, the relative risk of predicted morbidity is $\geq 2x$ more prevalent in patients with abnormal heart rate recovery (HRR), who we predict may constitute up to 50% of the patient population. If 50% abnormal HRR patients sustain postoperative morbidity compared with 30% patients exhibiting normal HRR preoperatively, with power =80%, 339 patients per group would be required to detect this difference in postoperative morbidity ($\alpha=0.05$). Since two sites are collecting data to demonstrate that this is not a site-specific phenomenon, the total number of patients is therefore 1356 (retrospective and prospective studies).

Surgical Patients – Statistical analysis

The primary analysis is to examine the relationship between exercise-induced abnormal HRR and the development of postoperative morbidity. The chi-square test will be used for an initial comparison, and subsequently logistic regression will be used to examine HRR and additionally the effects of preoperative factors upon postoperative morbidity. The log rank test and Cox regression will be used for equivalent analyses for the length of stay in hospital. The unpaired t-test or Mann-Whitney test will be used to compare cellular and heart rate variables between patients with normal/ abnormal HRR.

Direct access to source data/documents

The investigator(s)/ institution(s) will permit trial-related monitoring, audits, REC review, and regulatory inspection(s), providing direct access to source data/documents. Trial participants are informed of this during the informed consent discussion. Participants will consent to provide access to their medical notes.

17. Ethics and regulatory requirements

The sponsor will ensure that the trial protocol, patient information sheet, consent form, GP letter and submitted supporting documents have been approved by the appropriate regulatory body and a main research ethics committee, prior to any patient recruitment. The protocol and all agreed substantial protocol amendments, will be documented and submitted for ethical and regulatory approval prior to implementation.

Before the site can enrol patients into the trial, the Chief Investigator or designee must apply for Site Specific Assessment from Trust Research & Development (R&D) and be granted written NHS R&D approval. It is the responsibility of the Chief Investigator or designee at each site to ensure that all subsequent amendments gain the necessary approval. This does not affect the individual clinician's responsibility to take immediate action if thought necessary to protect the health and interest of individual patients.

18. Definition of Responsibilities .

Position	Approved Responsibilities

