	
Monitoring of quality of data transcription
 
Data analysis
 
Writing committee: Preparation of material for peer review publication and presentation

Research Nurse
 
[name]
 
[name]
 
[name]
 
[name]
 
[name]
	
Maintenance of Site File
 
Maintenance of secure recruitment database
 
Informed consent
 
Availability to answer participant queries
 
Signing of consent form
 
Recording of demographic data on Case Report Form (CRF)
 
Recording of specified postoperative outcomes on CRF
 
Be available for audit and inspections

Patient representative
	
Provide Service User perspective
 
Protocol design Steering group
 
Preparation of patient information leaflets and informed consent forms

19. Monitoring plan for the trial

The trial will be monitored according to the monitoring plan agreed by the sponsor, based on the self-monitoring template risk assessment. It is the responsibility of the CI to ensure that the sponsor's self-monitoring template is completed throughout the trial every two months and submitted to the JBRU at the regularity determined by the sponsor's risk assessment of the trial

phase. It is the responsibility of the CI to determine the monitoring risk assessment and explain the rationale. The PI will also be required to complete this self-monitoring template and return the form at the same frequency, to the CI and sponsor in parallel for review. It is the CI's responsibility to ensure that any findings identified in a PI's monitoring report are actioned in a timely manner and any violations of GCP or the protocol reported to the sponsor immediately. Any urgent safety measures at either the CI or a PI site must be reported by that site Investigator within 3 days, as per UK Regulations.

20. Insurance

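### The protocol sets the study up as unblinded and nothing in it keeps outcome recorders from HRR or HRR classifiers from the outcome, leaving an avoidable risk of differential error

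*Protocol*

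**What the plan says.** The type-of-trial line in the synopsis covers both parts: "Unblinded, two-site, observational retrospective and prospective studies in elective surgical patients undergoing cardiopulmonary exercise testing (CPET) as part of their routine preoperative workup".

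- **Exposure.** Section 8 says of the prospective study: "All heart rate data is derived from cardiopulmonary exercise testing acquired data, performed as part of their routine preoperative workup". Section 16 compares normal with abnormal HRR, and says of the abnormal group: "who we predict may constitute up to 50% of the patient population". The protocol gives no cut-off.
- **Outcome.** Section 16: "Primary outcome is incidence of morbidity on postoperative day 5". Section 11: "Post Operative Morbidity Survey data is routinely collected at UCLH and Derriford, so represent standard of care at our institutions".
- **Who records it.** Among the research nurse's tasks in section 18 is "Recording of specified postoperative outcomes on CRF". The same list includes informed consent.
- **Retrospective part.** The synopsis says that both centres will provide "Anonymized data detailing cardiopulmonary exercise tests and postoperative morbidity/ length of stay that are collected and assessed routinely as part of clinical care".
- **Separation of roles.** The only one stated is in section 10: staff giving perioperative care take no part in consent. Section 15 has a code-breaking procedure that refers to treatment allocation. It masks no assessor here, since nothing is allocated.

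**The concern.** The primary analysis relates abnormal HRR to morbidity. If the person scoring morbidity knows the HRR class, or the person classifying HRR knows the outcome, errors in one variable can depend on the other. The stated hypothesis is that autonomic dysfunction predicts morbidity, so staff have an expected direction in mind. Error that followed that expectation would inflate the association. A larger sample or covariate adjustment would not remove it, and an analysis plan cannot undo it once it is in the data.

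The safeguard is easy in this design. The exposure is measured before surgery and the outcome on set days afterwards, by different means. Neither judgement needs the other variable.

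**Working it through.** **Where each kind of error can enter**

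| Part | Morbidity recorded knowing HRR | HRR classified knowing morbidity |
|---|---|---|
| Prospective | Possible: study staff record outcomes after the CPET, with no masking stated | Possible if HRR is classified after outcomes are in |
| Retrospective | Not by study staff: morbidity data already exist (section 8) | Possible: both kinds of data are supplied, with no order of derivation or linkage stated |

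**Size of the outcome-recording route**

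The protocol gives no figure for such bias, so there is none to reproduce. This is an illustration.

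Inputs from section 16:
- Total 1356 = 339 × 2 groups × 2 sites, retrospective and prospective together.
- With half the patients abnormal, the upper end of the prediction, n = 1356 / 2 = 678 per HRR group.
- Overall day-5 morbidity 40%; two-sided α = 0.05.

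(Whether 339 follows from the stated 50% and 30% is a separate question. Only the planned total is used here.)

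Assumptions:
- True morbidity is 40% in both groups, so there is no real association.
- Knowledge of abnormal HRR raises recorded morbidity by s = 3, 5 or 8 points in prospective abnormal-HRR patients.
- A share w of patients is prospective, the same in both HRR groups. The protocol does not state w.

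Formulas:
- p₂ = 0.40, p₁ = 0.40 + w·s, d = p₁ − p₂, p̄ = (p₁ + p₂)/2
- SE₀ = √[2p̄(1 − p̄)/n]
- SE₁ = √{[p₁(1 − p₁) + p₂(1 − p₂)]/n}
- Chance of significance = Φ[(d − 1.96·SE₀)/SE₁] + Φ[(−d − 1.96·SE₀)/SE₁]

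Example, s = 5 points:
- w = 1: p₁ = 0.45, SE₀ = 0.02685, SE₁ = 0.02681. (0.05 − 1.96 × 0.02685)/0.02681 = −0.098, and Φ = 0.46. The other tail is negligible.
- w = 0.5: p₁ = 0.425, SE₀ = 0.02674, SE₁ = 0.02673. (0.025 − 1.96 × 0.02674)/0.02673 = −1.025, and Φ = 0.153. The other tail adds 0.002, giving 0.15.

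| Shift in prospective abnormal-HRR patients | w = 1 (upper bound) | w = 0.5 | w = 0.25 |
|---|---|---|---|
| 3 points | 20% | 9% | 6% |
| 5 points | 46% | 15% | 8% |
| 8 points | 84% | 32% | 12% |

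The nominal rate is 5%.

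**How much misrecording each shift needs**

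With 60% of patients truly free of morbidity, a shift of s requires a fraction s/0.60 of morbidity-free abnormal-HRR patients to be recorded as morbid:
- 0.03/0.60 = 5%
- 0.05/0.60 = 8%
- 0.08/0.60 = 13%

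Creating the whole planned 20-point difference (50% against 30%) in this way would need 0.20/0.60 = 33% misrecorded, even with every patient prospective.

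The HRR-classification route is not quantified, because the documents give nothing from which to size it.

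**The case against.** The strongest reply is that the word unblinded is being over-read. It stands in a type-of-trial line for a study without allocation, and section 12 calls randomisation not applicable. It may mean only that no treatment is masked. Masking of assessors and rules for deriving HRR could also sit in an analysis plan, a CRF or a working instruction. This stands as a limit: the protocol does not say that recorders are given HRR, nor that HRR is derived with outcomes in view. But unblinded is the only statement on masking, and the protocol text available sets nothing against it.

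Further points stand in part.

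- Morbidity is a routine survey at both sites, retrospective morbidity predates the study, and heart rate is read by instrument. These lower the risk. They do not remove it for prospective recording or for drawing the line between normal and abnormal.
- Ward staff may see the routine CPET report whatever the study does.

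Some stronger readings are tempting, and the documents do not support them.

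- A reader might infer from the nurse's list of tasks that whoever takes consent learns the HRR and then scores the same patient. Section 10 has patients approached before the CPET, when no HRR exists. Section 18 lists tasks for a role held by several people, and section 15 leaves individual duties to a delegation log.
- A reader might infer that retrospective CPET and morbidity data arrive as one joined file. The text says only that both are provided.
- A reader might treat bias towards the hypothesis as certain. It is a risk, and the documents contain no evidence that it occurs.
- A reader might apply the 20%, 46% and 84% to the study as planned. They assume that every patient is prospective, whereas the total includes retrospective patients.

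**Conclusion.** The point holds as an avoidable weakness of design. Nothing in the protocol text available masks prospective outcome recorders to HRR, or HRR classifiers to the outcome, although the two measurements are separate in time and method. Differential error could contribute part of the association. The amount of misrecording needed makes it unlikely to produce all of a 20-point difference.

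For the outcome-recording route alone, the w = 1 column above is the upper bound and the half-prospective column a more moderate case. Both rest on assumed shifts and an assumed split. The calculation shows that modest differential recording would matter if it occurred. It does not show that it occurs. The change is worth making because it is cheap, not because the study is shown to be biased.

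**What to change.** Replace the word unblinded in the type-of-trial line with a statement to this effect:

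1. Existing staff without access to morbidity or length of stay derive and classify HRR, and the values are locked before linkage to outcomes.
2. The outcome CRF carries no CPET result, and study staff recording prospective outcomes are not given the HRR value or class.
3. Retrospective CPET and outcome data are supplied as two files sharing a non-identifying study number assigned by the clinical team. They are joined only after HRR is locked.

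No added staff and no exchange of traces between sites are needed. The cost is slightly more data handling: two retrospective files instead of one, and a linkage number assigned before submission, whereas section 15 describes coding of submitted data. Ward staff cannot be fully masked to the routine CPET report, so the statement should claim masking only for study staff who record outcomes or classify HRR.

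### The immune comparison between HRR groups is unadjusted and eligibility does not explicitly exclude immune-modifying treatment or disease, so a leukocyte difference may reflect those exposures and not vagal function

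*Protocol*

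**What the plan says.** **Eligibility (Protocol, section 10).** One set of criteria serves the whole study: "All surgical patients referred for cardiopulmonary exercise testing preoperatively by their primary surgeon or anesthesiologist undergoing major noncardiac surgery". The exclusions are "history of exercise induced angioedema", pregnancy, and "any contraindication to cardiopulmonary exercise testing (as outlined by American Association of Anaesthesia"), after which the text shows no list. The immune sub-study has no criteria of its own.

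**Sampling and endpoints (section 8).** In the prospective part, "Blood derived immune cells will be acquired at UCLH site only pre and post exercise". The laboratory work is described as follows: "Ex-vivo laboratory studies will explore bioenergetic (mitochondrial) function in leukocyte subsets and Immune function in leukocyte subsets". No size or sampling rule is given for this sub-study.

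**Analysis (section 16).** For the cellular endpoints, "The unpaired t-test or Mann-Whitney test will be used to compare cellular and heart rate variables between patients with normal/ abnormal HRR". The same paragraph plans logistic regression including preoperative factors for morbidity, and Cox regression for the equivalent analysis of length of stay.

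**Interpretation.** The secondary objective in the trial summary is whether abnormal heart rate dynamics "is related to immune-inflammatory phenotypes and structural heart differences". Section 6 gives the reading to be placed on HRR: "The rate of heart rate recovery following exercise reflects how well the vagus nerve works". Section 7 states the need to link vagal neuro-immune activation to postoperative complications.

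**The concern.** HRR groups are formed by observation; section 12 confirms that nothing is randomised. Any characteristic that differs between the groups and also alters leukocytes will therefore appear as an HRR difference unless the analysis accounts for it. Recent chemotherapy, systemic steroids, other immunosuppressants, and haematological or autoimmune disease can be expected to act on the cells being assayed, and the eligibility text does not explicitly set any of them aside. Neither a t-test nor a Mann-Whitney test takes covariates.

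Section 16 plans regression with preoperative factors for the clinical outcomes but only a two-group test for the cellular ones. The cellular comparison is the part of the study that would support a neuro-immune reading of HRR. If one of these exposures is also associated with slow heart rate recovery, the planned test cannot tell its effect from that of vagal function.

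**Working it through.** The protocol gives no figure for the size of the immune sub-study, for the frequency of these exposures, or for their effect on leukocyte measures. Its only sample-size calculation concerns morbidity and does not bear on this point. All inputs below are assumptions.

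**Bias of the unadjusted comparison.** Let pA and pN be the shares exposed in the abnormal and normal HRR groups. Let D be the shift in a cellular measure caused by exposure, in units of its SD among patients with the same exposure status. With no true HRR effect:

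- bias = D × (pA − pN)
- variance in a group = 1 + D² × p(1 − p)
- z = bias / √[(varA + varN)/n], with n per group
- rejection probability = P(Z > 1.96 − z) + P(Z < −1.96 − z)

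**Illustration: pA = 0.30, pN = 0.15, D = 1**

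- bias = 1 × (0.30 − 0.15) = 0.15 SD
- varA = 1 + 0.30 × 0.70 = 1.21; varN = 1 + 0.15 × 0.85 = 1.1275; sum = 2.3375

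| n per group | SE = √(2.3375/n) | z | Rejection probability |
|---|---|---|---|
| 50 | 0.216 | 0.69 | 0.107 |
| 100 | 0.153 | 0.98 | 0.165 |
| 200 | 0.108 | 1.39 | 0.284 |

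**Range at 100 per group, D from 0.5 to 1.5**

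| pA vs pN | Bias (SD) | Rejection probability |
|---|---|---|
| 10% vs 10% | 0 | 5% |
| 15% vs 10% | 0.025 to 0.075 | 5% to 8% |
| 20% vs 10% | 0.05 to 0.15 | 6% to 16% |
| 30% vs 10% | 0.10 to 0.30 | 11% to 45% |

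The bias depends entirely on the imbalance. With equal shares there is none, however large D is. With unequal shares the bias does not shrink as patients are added, so the false-positive rate rises with n.

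**Restriction or adjustment?** Use the illustration at 100 per group (30 and 15 exposed, 70 and 85 unexposed).

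- Unadjusted, all patients: SE = √(2.3375/100) = 0.153 SD, with bias 0.15 SD.
- Restricted to unexposed patients: SE = √(1/70 + 1/85) = 0.161 SD, no bias from exposure. This is 0.161/0.153, about 5.6% wider before rounding.
- All patients, adjusted for exposure (common HRR difference, SD 1 within each exposure stratum): information = 70 × 85/155 + 30 × 15/45 = 38.39 + 10.00 = 48.39; SE = 1/√48.39 = 0.144 SD, no bias from exposure.

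Under these assumptions both routes remove the bias, but restriction costs precision and adjustment in all sampled patients does not.

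**The case against.** **The confounding is assumed.** The protocol mentions none of these exposures and gives no link between them and HRR. This stands. A reader might infer that the immune result will be confounded, or that exposed patients are known to be commoner in the abnormal-HRR group. The documents support neither statement, only that the stated method has no protection if the imbalance exists.

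**The objective is association.** The secondary objective asks whether heart rate dynamics are related to immune phenotypes, and an unadjusted comparison answers that as worded. The sentence in section 6 that calls the study mechanistic goes on to speak of identifying patients at risk of complications, which is the morbidity question. Both points are fair. But sections 6 and 7 also read HRR as vagal function and look for a neuro-immune link, and an unadjusted association does not carry that reading.

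**Who is sampled.** A reader might infer that every eligible UCLH patient enters the sub-study, including those with active infection. The text does not say so. Samples come from prospective, consenting patients, and the contraindication list is not shown and may cover some infections. Infection is therefore best described as not explicitly excluded.

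**Adjustment belongs in a SAP, and the CRF is not shown.** Adjusted and sensitivity analyses could be added in a SAP, and it cannot be inferred that these items are missing from the CRF. But the protocol itself names the cellular test and itself sets eligibility, and no later plan can adjust for exposures that were not recorded. Section 18 mentions CRF recording only of demographic data and postoperative outcomes.

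**Pre- and post-exercise samples allow within-patient change.** Analysing change would remove stable baseline differences. The protocol does not name change as the variable, and change would not remove an effect of treatment on the response to exercise.

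**Precision.** A reader might expect that leaving exposed patients out would sharpen the comparison. On the illustration it does the opposite, so precision is no argument for restriction.

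**Conclusion.** The point holds as a weakness of the stated method for a secondary objective. Eligibility does not explicitly exclude the main immune-modifying treatments and diseases, and the cellular comparison between non-randomised HRR groups has no adjustment. If these exposures are unevenly spread, a leukocyte difference may reflect them and not vagal function.

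The size is unknown because the documents give no inputs. At 30% against 15% exposed with a 1 SD shift, the spurious difference is modest at 0.15 SD, but the nominal 5% test would be positive about 11% to 28% of the time at 50 to 200 per group. These figures rest on the assumed shares, the assumed shift, no true HRR effect and a normal approximation.

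The change should be made, because the exposures need to be captured at the time of the exercise test. The primary outcome, its sample size and the HRR-morbidity conclusion are unaffected.

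**What to change.** 1. Record at CPET, for each patient sampled at UCLH: recent chemotherapy or radiotherapy; systemic steroid or immunosuppressant use; active infection; haematological or autoimmune disease. Define the time window for recent treatment in advance.
2. In section 16, make the main immune comparison a linear model of each cellular measure on HRR group in all sampled patients, adjusted for these exposures and for age, sex and cancer. Transform the measure where its distribution requires it. State whether the variable is the pre-exercise value, the post-exercise value or the change.
3. Repeat the comparison in unexposed patients only, as a sensitivity analysis. The t-test or Mann-Whitney result can remain as a descriptive first step.
4. Leave eligibility and the HRR-morbidity analysis unchanged.

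The cost is a few CRF items, some amended analysis wording and a little more analysis. With a small sub-study or rare exposures, the individual exposures may need to be combined into one indicator to keep the model stable, and that rule should be fixed before the data are seen.
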